7.3.2 Laboratory Data

Clinical laboratory assessments for this study include: hematology, blood chemistry including liver function tests (LFTs), coagulation, urinalysis and immunoglobulin. Values will be analysed after conversion into standard international units, where applicable. A complete listing of all laboratory parameters with normal ranges is included in [Appendix 1](#).

Applicable laboratory data will be graded according to NCI-CTCAE Version 4.03. Shift from baseline to maximum post-baseline grades will be tabulated for hematology, blood chemistry including liver function test (LFT), and coagulation.

Post-baseline lab values used in summary tables for shift in grades, and LFT elevations will include lab tests performed after the start of the first dose of study treatment, up to 30 days post last dose.

Laboratory parameters will be presented as follows:

- Shift from baseline to maximum post-baseline CTCAE grade for hematology laboratory parameters
- Shift from baseline to maximum post-baseline CTCAE grade for chemistry laboratory parameters
- Shift from baseline to maximum post-baseline CTCAE grade for coagulation laboratory parameters
- New grade ≥ 3 hematology laboratory parameters
- New grade ≥ 3 chemistry laboratory parameters
- By visit summary of change from baseline for immunoglobulin parameters

- Listing of subjects with AST or ALT >3xULN in combination with total bilirubin >2xULN. The elevations of ALT/AST and total bilirubin must occur within 2 days of each other.
- Listing of all laboratory values
- Listing of laboratory parameters with grade 3 or higher CTCAE grades.
- Listing of selected hematology laboratory parameters with CTCAE grades
- Listing of selected LFTs with CTCAE grades

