	
considered as “early progression” subjects and, therefore, should be considered evaluable.
 
Primary Efficacy Analysis
 
ORR will be tested against the null ($\leq 30\%$) by 1-sided exact binomial test at the 0.025 level. The estimated ORR along with the 2-sided 95% exact confidence interval will be provided. Missing data will be imputed by assuming that any subjects not exhibiting a response (CR or PR) are non-responders.

--	---

Table 1: Study Assessments for IPI-145 Monotherapy

	Screening Day -30 to -1	Cycle 1, Cycle 2 & Cycle 3 (28-Day Cycle Length)		Cycle 4, Cycle 5, Cycle 6 & Cycle 7 (28-Day Cycle Length)	Cycle 8 and beyond – every second cycle (28-Day Cycle Length)	End of Treatment (EoT) (within 7 days following the decision to discontinue study treatment) ^s	Safety Follow-up (30+7 days from last dose) ^t
		Day		Day	Day		
		1 (±4) ^u	15 (±3)	1 (±4)	1 (±4)		
Informed Consent	X						
Inclusion/Exclusion Criteria	X						
Histologic confirmation of indolent B-cell lymphoma (FL, MZL, or SLL)	X ^a						
Medical History, Demographics	X						
Cancer History	X						
Follicular Lymphoma International Prognostic Index (FLIPI) score at time of Screening	X						
Hepatitis Serology, CMV/EBV serology or viral load, HIV	X ^b						
Physical Examination/Vital Signs ^d	X ^c	X	X	X	X	X	
ECG (12-lead)	X	See Table 2					
Bone marrow biopsy and/or bone marrow aspiration	X ^e	See Table 3					
CT scans of the chest, abdomen and pelvis	X ^f	See Table 3					
ECOG Performance Status	X						
B symptoms	X	X		X	X		
Serum/Urine βhCG Pregnancy Test	X ^g	X ^g		X ^g	X ^g		
Blood chemistry ^j	X ^{c,h}	X ^h		X ^h	X ^h	X ^h	
Liver Function Tests ^j	X ^{c,i}	X ⁱ	X ⁱ	X ⁱ	X ⁱ	X ⁱ	
Hematology ^j	X ^{c,k}	X ^k	X ^k	X ^k	X ^k	X ^k	
Coagulation ^j	X ^{c,l}	X ^l					
Urinalysis ^j	X ^{c,m}	X ^m		X ^m			
Prior/Concomitant Medications ⁿ	X	X	X	X	X	X	X ^t
Prior/Concomitant Procedures ^o	X	X	X	X	X	X	X ^t
AE/SAE Assessment	X ^p	X	X	X	X	X	X ^t
Quality of Life (QoL) (EQ-5D)	X ^q	X ^q		X ^q	X ^q	X ^q	
Drug Self-administration Diary		X		X ^r	X ^r	X ^r	
IPI-145 Administration		X ^r					

- a. Histologic confirmation based on biopsy obtained <36 months prior to Cycle 1, Day 1 should be performed unless medically contraindicated. For subjects who progressed within 2 months of initiating most recent chemotherapy, a repeat biopsy to confirm histology should be performed.

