- i. Liver function tests to include lactate dehydrogenase (LDH), serum alanine aminotransferase (ALT), serum aspartate aminotransferase (AST), total and direct bilirubin, and alkaline phosphatase (ALP). If the Screening liver function tests are performed within 7 days of Cycle 1, Day 1 then these Screening results can be used in place of the Cycle 1, Day 1 liver function tests results. Blood samples should be drawn and results reviewed within 72 hours prior to the clinic visit. All clinically significant laboratory findings, including but not limited to those findings resulting in a drug interruption/reduction/discontinuation or requiring medical intervention should be reported as an AE (see protocol [Section 8.1.1](#) for definition of an AE).
- j. Additional (unscheduled) assessments should be done as clinically indicated.

- k. Hematology laboratory parameters to include: hemoglobin, hematocrit, platelets, and white blood cell count with 5-part differential (manual or automated) [for an absolute neutrophil count (ANC), neutrophils, lymphocytes and monocytes, eosinophils and basophils]. If the Screening hematology evaluations are performed within 7 days of Cycle 1 Day 1, then these Screening results can be used in place of the Cycle 1 Day 1 hematology results. Blood samples should be drawn and results reviewed within 72 hours prior to the clinic visit. Clinically significant laboratory findings, including but not limited to those findings resulting in a drug interruption/reduction/discontinuation or requiring medical intervention should be reported as an AE (see protocol Section 8.1.1 for definition of an AE).
- l. Coagulation evaluation will occur at Screening and on Day 1 of Cycles 1, 2, and 3 for all subjects. Coagulation laboratory parameters include prothrombin time (PT), international normalized ratio (INR) and activated partial thromboplastin time (aPTT). If the screening coagulation evaluations are performed within 7 days of Cycle 1 Day 1, these Screening results can be used in place of the Cycle 1 Day 1 coagulation results. Blood samples should be drawn and results reviewed within 72 hours prior to the clinic visit. Clinically significant laboratory findings including but not limited to those findings resulting in a drug interruption/reduction/discontinuation or requiring medical intervention should be reported as an adverse event (see protocol [Section 8.1.1](#) for definition of an AE).

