- Cardiac: Subjects who develop new Grade 3 or higher cardiac events should have IPI-145 held until resolution of symptoms. This includes new Grade 3 QTcF prolongation only if >20 ms increase from Baseline. A new Grade 3 QTcF prolongation (>20 ms from baseline) requires triplicate ECGs with the average measurement used and the use of Fridericia's correction method (QTcF). For subjects with a right or left BBB, a new Grade 3 QTc prolongation is defined as an increase in QTcF of >100 ms from the pre-dose ECG to any post dose ECG as the QRS interval is prolonged at Baseline (by approximately 40 ms) in subjects with a BBB

Subjects requiring treatment interruption should be re-evaluated at least weekly until the toxicity improves to \leq Grade 1 or returns to Baseline level. IPI-145 dose will be restarted at doses described in [Table 7](#).

Treatment Interruption for Hematologic Toxicity

Worsening or transient Grade 3 or higher neutropenia, anemia, and/or thrombocytopenia caused by the subject's existing disease or by IPI-145 are to be expected. Blood counts should be monitored as described in the protocol with the frequency increased as clinically indicated in the setting of new or worsening Grade 3 or higher cytopenias. IPI-145 dosing may be interrupted at any time, at the discretion of the treating physician.

Treatment with IPI-145 should be interrupted for the following symptomatic hematologic toxicities:

- Grade 3 or higher febrile neutropenia
- Grade 3 or higher thrombocytopenia associated with Grade 2 or higher hemorrhage

**Protocol IPI-145-06
IPI-145****Verastem, Inc.**

The subject should be re-evaluated at least weekly until the toxicity improves to \leq Grade 1 or returns to Baseline.

A dose may be withheld up to 42 days for toxicity. Doses withheld for >42 days due to treatment-related toxicity will result in permanent discontinuation from treatment. Any subject who requires reduction to less than 10 mg BID due to repeat occurrence of the same treatment-related toxicity will be permanently discontinued from treatment. Any subject who requires reduction to less than 5 mg BID for different treatment-related toxicities will be permanently discontinued from study treatment. Dose levels are shown in [Table 7](#).

Table 7: IPI-145 Dosing Levels

Dose Level	Dose (mg)
1	25 BID
-1	15 BID
-2	10 BID
-3	5 BID

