8.2.3.2 Immediate Reporting of Medical Events of Interest

Reports or laboratory results of **AST or ALT >3x ULN in combination with bilirubin >2x ULN are medical events of interest**, and therefore immediately reportable events, even if the events do not meet serious adverse event criteria.

Clinical findings of **Grade 3 or higher rash are medical events of interest**, and therefore immediately reportable events, even if the events do not meet serious adverse event criteria. Pre-existing skin conditions that recur would not meet this definition unless the recurrence is of a greater severity/frequency than previously experienced.

All medical events of interest will be reported to the Sponsor or designee within 24 hours of the Investigator's first knowledge of the event, even if the experience does not appear to be related to IPI-145. Medical Events of Interest should be communicated on the Verastem SAE / MEOI report form as described above for SAEs.

Any occupational exposure or exposure of an individual not enrolled in the study to the investigational medicinal product must be reported to the Sponsor or designee within 24 hours of the Investigator's first knowledge of the event, even if the exposure does not result in an AE. Unintentional exposures should be communicated on the SAE/MEOI report form, as described above for SAEs.

8.2.3.3 *Reporting of Serious Adverse Events to the Institutional Review Board (IRB)/Ethics Committee (EC)*

Verastem or designee shall notify the Investigator and/or the IRBs/ECs per institutional guidelines of potential serious risks from clinical trials or any other sources, including the following:

- Suspected adverse reaction that is both serious and unexpected.
- Any findings from other studies that suggest a significant risk in humans exposed to the drug.
- Any finding from animal or in vitro testing that suggest a significant risk to humans exposed to the drug, such as mutagenicity, teratogenicity, or carcinogenicity; or report of significant organ toxicity at or near the expected human exposure.

Verastem or designee shall notify the Central Ethics Committees (CEC) of new serious, related and unexpected AEs or significant risks to subjects, per local country requirements.

The Investigator will also notify the IRB/ Local Ethics Committee (LEC), of serious, related and unexpected AE(s) or significant risks to subjects per local country requirements.

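### The SAP's combined liver listing adds a 2-day limit that the protocol does not state, and can omit subjects whose ALT/AST and bilirubin elevations never fall close together

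*SAP*

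**What the plan says.** SAP 7.3.2 (Laboratory Data) includes this output: "Listing of subjects with AST or ALT >3xULN in combination with total bilirubin >2xULN". It then restricts it: "The elevations of ALT/AST and total bilirubin must occur within 2 days of each other". No reason is given for 2 days. The section does not say whether *occur* refers to any two qualifying values or to the dates on which each threshold was first crossed. The same section sets the observation period: "LFT elevations will include lab tests performed after the start of the first dose of study treatment, up to 30 days post last dose".

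Protocol 8.2.3.2 uses the same thresholds for 24-hour reporting: "AST or ALT >3x ULN in combination with bilirubin >2x ULN are medical events of interest". It states no time window, and it applies even when the event is not serious.

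Protocol Table 1 schedules liver function tests on Days 1 and 15 of Cycles 1 to 3, on Day 1 of Cycles 4 to 7, on Day 1 of every second cycle from Cycle 8, and at end of treatment. Its footnotes put ALT, AST and total bilirubin in one panel, allow the blood to be drawn up to 72 hours before the visit, and allow unscheduled tests when clinically indicated. During a toxicity hold, Protocol 4.2 says: "Subjects requiring treatment interruption should be re-evaluated at least weekly until the toxicity improves to" Grade 1 or lower, or returns to baseline. Under SAP 6.8, unscheduled results enter listings.

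**The concern.** The listing and the medical event of interest share their thresholds but not their timing. A case reported under the protocol can therefore be absent from the SAP output built on the same criterion, and no reconciliation of the two is planned.

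The window also does not match the sampling. If two samples are almost never taken within 2 days, a rule that appears to allow a short lag between the elevations in practice allows none, except where extra draws were taken.

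What is at stake is which subjects the study report identifies as having had a combined elevation. The other liver outputs in SAP 7.3.2 are grade shifts and new Grade 3 or higher tables by parameter, and listings of values; none joins the two criteria. The adverse event outputs in SAP 7.3.1 include no listing of medical events of interest. Because such an event need not be serious, the serious adverse event listing need not show it. ALT/AST elevation was the most common related Grade 3 or higher event among the Phase 1 iNHL subjects (Protocol 1.3.3.2), so this is a listing that readers will look for.

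**Working it through.** The 2-day limit is a definition, so there is no derived figure of the plan's to reproduce. The check is date arithmetic on Protocol Table 1, followed by applying the rule to possible courses.

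**Step 1. Inputs.** Day 1 visits have a window of ±4 days (none for Cycle 1 Day 1) and Day 15 visits ±3 days. The early-draw allowance is 72 hours, that is 3 days.

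**Step 2. Formula.** Smallest gap between consecutive scheduled draws = nominal gap − window of earlier visit − window of later visit − 3 days (early draw at the later visit).

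| Consecutive draws | Pairs | Nominal gap (days) | Smallest gap (days) |
|---|---|---|---|
| C1D1 to C1D15 | 1 | 14 | 14 − 0 − 3 − 3 = 8 |
| Other pairs, C1D15 to C4D1 | 5 | 14 | 14 − 3 − 4 − 3 = 4 |
| C4D1 to C8D1 | 4 | 28 | 28 − 4 − 4 − 3 = 17 |
| C8D1 to C18D1 | 5 | 56 | 56 − 4 − 4 − 3 = 45 |

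Of the 15 pairs from C1D1 to C18D1, none can fall within 2 days. Weekly re-evaluation during a hold (7 days) also exceeds 2 days. Only unscheduled draws, holds checked more often than weekly, or an end-of-treatment draw taken close to another draw can give two different samples inside the window.

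**Step 3. Would another fixed window do?** Pairs that could qualify at nominal timing: 7-day window, 0 of 15 (5 of 15 with the most favourable windows and early draw); 14-day, 6 of 15; 28- or 30-day, 10 of 15; 56-day, 15 of 15. Any fixed window shorter than 56 days therefore works differently in different parts of the schedule.

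**Step 4. Apply the rule to weekly checks during a hold.** Suppose ALT is above 3x ULN at the first check.

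| Course | Any-pair reading | Onset-date reading |
|---|---|---|
| Both thresholds first crossed in the same sample | Listed | Listed |
| Bilirubin crosses 7 days later, ALT still above 3x ULN | Listed (one sample holds both) | Not listed (7 > 2) |
| Bilirubin crosses 7 days later, ALT and AST then at or below 3x ULN | Not listed (7 > 2) | Not listed (7 > 2) |

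The third course is lost under either reading. The second depends on a word that the SAP does not define, so two programmers could produce different listings from the same data.

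**The case against.** Several points on the other side are sound.

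- **Overlap is captured.** A reader might infer that every bilirubin rise lagging by 3 days or more is missed. That does not follow. Under the any-pair reading, a late bilirubin rise qualifies if ALT or AST is still above 3x ULN in that sample. Only elevations that never come within 2 days of each other are lost.
- **Same-sample is not absolute.** Unscheduled draws are allowed and enter listings, and weekly is a minimum during a hold. Subjects with a liver signal are the likeliest to have closely spaced draws. This stands, although the plan guarantees no such draws.
- **No count follows from Phase 1.** A reader might scale the Phase 1 rates of related Grade 3 or higher ALT/AST elevation (34% of iNHL subjects, 40% at 25 mg BID) to 120 subjects and treat the result as the number at risk of omission. Those rates concern transaminases alone. The documents give no rate of combined elevation, still less of combined elevation without overlap.
- **The protocol's silence is not an explicit rule of any time.** Near-concurrence is a natural reading of a combined criterion, and Protocol section 9 leaves statistical detail to the SAP. So this is a difference to reconcile, not a flat contradiction. But the SAP neither explains 2 days nor relates it to the sampling interval.
- **An open window brings in noise.** Treatment can run past 13 cycles, and raised bilirubin from Gilbert's syndrome is permitted at entry, so unrelated pairs could be listed. This is a fair cost, and displaying the dates and baseline bilirubin deals with it.
- **Nothing is hidden from surveillance.** Expedited reporting does not depend on the listing, and all values are listed elsewhere. This is correct and limits the severity.

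**Conclusion.** The point holds in a limited form. On scheduled cycle-visit draws the 2-day rule amounts to a same-sample rule: 0 of 15 pairs can fall within it, and the smallest possible gap is 4 days. Subjects whose bilirubin exceeds 2x ULN more than 2 days from every ALT/AST value above 3x ULN are absent from the only planned output that combines the criteria, although the protocol states no such limit for its medical event of interest. If *occur* means onset dates, even a subject with both values elevated in one sample could be omitted.

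The number of subjects affected cannot be computed from the documents, may be small and could be zero. The conclusion assumes draws on the Table 1 schedule; extra draws reduce the loss by an unknown amount. It concerns one descriptive safety listing and changes no hypothesis test, efficacy estimate or expedited report. The correction is still worth making because it is cheap and alters which subjects are identified.

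**What to change.** In SAP 7.3.2, replace the 2-day sentence with a definition along these lines:

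- List every subject with at least one AST or ALT value above 3x ULN and at least one total bilirubin value above 2x ULN, each taken after first dose and up to 30 days after last dose, counting any qualifying pair of values.
- For each subject show baseline bilirubin, the dates of both elevations (using the closest qualifying pair) and the days between them.
- Flag pairs within 2 days, so that the present definition survives as a visible subset.
- Reconcile the listing with the medical events of interest reported under Protocol 8.2.3.2, and explain any subject who appears in only one of the two.

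This needs no new data: a short SAP edit, some programming and one reconciliation. The downside is that a few unrelated pairs may appear, for example long gaps or chronically raised bilirubin; the dates and baseline value let the reader discount them.

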7.3.3 Vital Signs

Vital signs will be presented in individual subject data listings, and will not be summarized by visit.

7.3.4 Electrocardiogram (ECG)

ECG data and change from baseline will be descriptively summarized by visit. The frequency and percentage of subjects meeting the following criteria will be summarized by visit:

- QTcF (msec) categorized as:
 - ≤ 450
 - > 450 to ≤ 480
 - > 480 to ≤ 500
 - > 500
- Change from baseline in QTcF (msec):
 - ≤ 30
 - > 30 to ≤ 60
 - > 60

Subjects' QTcF values for each of the summaries above will be the arithmetic mean of the triplicate measures taken at each respective timepoint.

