- s. An End of Treatment (EoT) visit is to be performed for all subjects who permanently discontinue study treatment within 7 days following the decision to discontinue study treatment. EoT assessments need not be repeated if performed within the previous 14 days, or 30 days for CT scan.
- t. All subjects will have a Safety follow-up visit approximately 30 (+7) days after the last dose of study drug. If possible, this visit should occur prior to the initiation of any subsequent anticancer therapy. Assessments should include collection of AEs/SAEs and concomitant medications/procedures. This can be performed by telephone call, as long as the subject does not require laboratory and/or other procedures related to any new or ongoing AEs, in which case a clinical visit will be required.

Protocol IPI-145-06
IPI-145

Verastem, Inc.

- u. Visit window does not apply to Cycle 1, Day 1.

Table 2: Pharmacokinetic and Biomarker Assessments

Time (hr) relative to IPI-145 administration	Cycle 1 (28-Day Cycle Length)				Cycle 2 (28-Day Cycle Length)	Cycle 3 (28-Day Cycle Length)	Cycles 5, 7, 10 & 14 (28-Day Cycle Length)	End of Treatment (EoT) (within 7 days following the decision to discontinue study treatment)
	Day 1	Day 15 (±3)			Day 1 (±4)	Day 1 (±4)	Day 1 (±4)	
	Pre-dose	Pre-dose	+1	+4	Anytime during the visit	Anytime during the visit	Anytime during the visit	
Pharmacokinetic blood sample collection ^a		X ^b	X	X	X	X		
ECG (12-lead)	X ^c	X ^c	X ^c	X ^c				
Serum and plasma biomarkers	X	X			X	X	X	X
Immunoglobulin blood levels ^d	X					X	X	X
Immunophenotyping evaluations (e.g. B/T-lymphocyte panel) ^e	X				X	X	X	X
Archival tumor tissue ^f	X							
Optional pharmacogenomics blood sample ^g	X							
Optional tumor tissue biopsy (e.g. accessible involved lymph nodes) before treatment, on study, and at progression ^h	X	X						X ⁱ

- a. PK blood samples for IPI-145 plasma concentration determination will be collected from all subjects on Cycle 1 Day 15, Cycle 2 Day 1 and Cycle 3 Day 1. An additional blood sample for PK is requested at the start and end of any drug interruption/hold for an AE, when feasible.
- b. On Cycle 1 Day 15, the morning dose of study medication will be administered in the clinic in order to accommodate PK sampling.
- c. Assessment of the QT interval (for corrected QT [QTc] determination) will be performed as marked in the above table. All ECGs are to be performed in triplicate, within approximately a 5 minute time period

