6.3.3 B symptoms

B symptoms [fever (i.e., temperature $>38^{\circ}\text{C}$ [$>100.4^{\circ}\text{F}$]) for 3 consecutive days, weight loss exceeding 10% of body weight in 6 months, and/or drenching night sweats] will be assessed on each Day 1 clinic visit indicated in [Table 1](#).

6.3.4 12-Lead ECG

Assessment of the QT interval via ECGs will be performed at visits as indicated in [Table 1](#). All ECGs should be conducted following an approximate 10-minute rest period in a semi-recumbent or supine position and obtained in triplicate within approximately a 5 minute time period. QTc measurements will use the Fridericia's correction method (QTcF).

Any clinically significant change from baseline in ECG parameters will be captured as an AE, per [Section 8.2.1](#).

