3 STUDY DESIGN

3.1 OVERVIEW

Study IPI-145-06 is a Phase 2, open-label, single arm efficacy and safety study of IPI-145 administered orally to subjects diagnosed with iNHL (FL, MZL or SLL) whose disease is refractory to rituximab and to either chemotherapy or RIT. The study population consists of adult male and female subjects who meet the inclusion/exclusion criteria, enrolled at up to approximately 100 sites worldwide.

All subjects enrolled will be assigned to the same treatment of 25 mg IPI-145 orally twice daily (BID) administered continuously in 28-day treatment cycles for up to 13 cycles. To receive additional cycles of IPI-145 beyond 13 cycles, subjects must have documented evidence of response (CR or PR) or stable disease (SD) at the Cycle 14 Day 1 response assessment according to the revised International Working Group (IWG) criteria. These subjects may continue to receive IPI-145 treatment until disease progression or unacceptable toxicity.

All subjects who permanently discontinue treatment with IPI-145 for reasons other than withdrawal of consent from overall study participation will enter survival follow-up. Survival follow-up will occur every 6 months (± 4 weeks) from permanently discontinuing IPI-145 treatment for up to 3 years after first dose of IPI-145 or until death.

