6.8 UNSCHEDULED VISITS

Unscheduled visits will only be included in listings and in post-baseline summaries of extreme values. Unless otherwise specified, unscheduled visits will not be included in the by-visit summaries.

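### QTcF values from unscheduled visits after Cycle 1 Day 15 never enter the SAP's QTcF category tables, and no per-subject worst post-baseline summary or ECG listing is planned

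*SAP*

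**What the plan says.** ECG measures are a named secondary safety endpoint (Protocol 3.2; SAP 5.4). Four places decide what is reported about them.

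- **The tables.** SAP 7.3.4 states that "ECG data and change from baseline will be descriptively summarized by visit" and, for the QTcF bands, that "The frequency and percentage of subjects meeting the following criteria will be summarized by visit". The bands are 450, 480 and 500 ms for the value, and 30 and 60 ms for the change from baseline. The QTcF used is the mean of the triplicate at a timepoint.
- **Unscheduled data.** SAP 6.8 says "Unscheduled visits will only be included in listings and in post-baseline summaries of extreme values", and that unless otherwise specified "unscheduled visits will not be included in the by-visit summaries".
- **The schedule.** Protocol Table 1 has an ECG at Screening and then refers to Table 2, whose footnote says "Assessment of the QT interval (for corrected QT [QTc] determination) will be performed as marked in the above table". The marks are Cycle 1 Day 1 pre-dose and Cycle 1 Day 15 pre-dose, +1 h and +4 h. There are none in later cycles and none at End of Treatment.
- **Later ECGs.** Protocol 4.2 foresees them: "A new Grade 3 QTcF prolongation (>20 ms from baseline) requires triplicate ECGs with the average measurement used". Protocol 6.3.4 adds that "Any clinically significant change from baseline in ECG parameters will be captured as an AE".

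**The concern.** Read together, these rules confine the QTcF category tables to one post-baseline visit early in treatment. A later ECG, taken because of a symptom or a suspected prolongation, is the kind most likely to show a large value. Its millisecond reading has no place in the tables built to show large values.

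The study report could then show no subject in the above-500 ms row while the adverse event tables show a drug interruption for QT prolongation. A reader could not reconcile the two from the tables. A late value that the investigator did not judge clinically significant would not surface in any output the SAP names.

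A smaller gap sits within Day 15. Each subject has three post-baseline readings at that visit, and the SAP does not say how they give one count of subjects who crossed a cut.

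**Working it through.** The plan gives no figure to reproduce here, so the check sets the provisions side by side. The only arithmetic is on the schedule.

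**Step 1: which ECGs are scheduled after baseline?** SAP 6.7 defines baseline as the most recent value before first dose, so the Screening and Cycle 1 Day 1 pre-dose ECGs are baseline candidates. The scheduled post-baseline ECGs are the three readings at Cycle 1 Day 15, all at one visit.

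**Step 2: what can enter the category tables?** SAP 7.3.4 is by visit. The SAP 6.8 default excludes unscheduled visits, and SAP 7.3.4 does not say otherwise. SAP 6.8 does open a route through post-baseline extreme-value summaries, but SAP 7.3.4 plans none for ECG. It also opens a route through listings, but the SAP names no ECG listing. For comparison, SAP 7.3.2 names several laboratory listings and SAP 7.3.3 names one for vital signs.

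**Step 3: where does a QTcF value from a later unscheduled visit go?**

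| Later QTcF value | QTcF category table | TEAE tables | Named ECG listing |
|---|---|---|---|
| Judged clinically significant, recorded as an AE | No | Yes, by preferred term and grade; also under interruption, reduction or discontinuation where that applies | None |
| Not recorded as an AE | No | No | None |

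The TEAE tables cover first dose to 30 days after last dose (SAP 7.3.1). They carry no millisecond bands.

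**Step 4: how early does scheduled ECG collection stop?** Treatment is "administered continuously in 28-day treatment cycles for up to 13 cycles", and longer for subjects with CR, PR or SD.

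- Initial course: 13 x 28 = 364 days.
- Last scheduled ECG at Day 15: 15 / 364 = 4.1%.
- Over the visit window of 3 days either side: 12 / 364 = 3.3% to 18 / 364 = 4.9%.

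Many subjects will be treated for less time. The protocol gives two Phase 1 medians at 25 mg BID, 9.8 cycles (Section 1.3.3.2) and 4.7 cycles (Section 1.5). With Day 18 as the last ECG:

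- 9.8 x 28 = 274.4 days, and 18 / 274.4 = 6.6%.
- 4.7 x 28 = 131.6 days, and 18 / 131.6 = 13.7%.

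On any of these figures, most treatment time has no scheduled ECG.

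**Step 5: the Day 15 count.** SAP 7.3.4 says by visit and refers to timepoints only when describing the averaging of triplicates. If the three readings became three rows, the number of subjects ever above a cut would lie between the largest row and the sum of the rows. If they were reduced to one value per subject, the result would depend on whether that value is the maximum, the mean or one chosen reading. The SAP specifies neither.

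**The case against.** **The adverse event route.** A reader might infer that a late QTcF prolongation reaches no table at all. The documents do not support that. Protocol 6.3.4 sends clinically significant ECG changes to AE reporting, and SAP 7.3.1 tabulates TEAEs by grade and by effect on dosing. The dose-hold rules in Protocol 4.2 are framed around adverse events at least possibly related to study drug, so a hold should show in the TEAE interruption table. This stands, and it narrows the point to the value-based counts. It does not remove it: AE reporting depends on the investigator's judgement of significance and gives no 500 ms or 60 ms count.

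**ECG is not alone.** SAP 7.3.2 uses maximum post-baseline grades for hematology, chemistry and coagulation, so a reader might infer that only ECG is left without a worst-value summary. That is not so. Immunoglobulins are summarized by visit only, and vital signs are only listed. The laboratory tables show a workable model already in the SAP, not a rule that ECG alone breaks.

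**Unscheduled visit or extra ECG?** SAP 6.8 speaks of visits. An additional ECG taken at a scheduled visit, such as Cycle 4 Day 1, is not clearly excluded. This stands: the certain exclusion covers unscheduled visits, and the extra-ECG case is unsettled.

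**The schedule sets the coverage.** The 3.3% to 4.9% comes from when ECGs are collected, and a new table does not change that. A worst-value row would combine complete Day 15 data with ECGs from a selected few. Both points stand and call for a footnote.

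**Low stakes.** Protocol 9.5 asks only for ECG changes over time, no test or decision rule uses the outlier counts, and Section 1.3.3.1 reports no clinically significant ECG abnormalities in the first-in-human study. It would be wrong to infer from this point that a QT signal exists. The case rests on complete reporting of a named endpoint.

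**Conclusion.** The concern holds in a limited form. Followed as written, the SAP leaves QTcF values from unscheduled visits after Cycle 1 Day 15 out of the QTcF category tables. Only those reported as AEs are tabulated, by preferred term and grade. The any-time count across the three Day 15 readings is undefined.

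The effect is on the reported above-500 ms and above-60 ms counts for a secondary safety endpoint. Efficacy conclusions are untouched. The number of subjects affected cannot be worked out, because the documents do not say how many later ECGs will be taken; it could be none.

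The conclusion assumes that Table 2 as it appears in the text shows every scheduled on-treatment ECG, that no separate table shells already contain a worst-value ECG summary or an ECG listing, and that the SAP 6.8 default applies because SAP 7.3.4 does not override it. It is worth correcting because the summary needed is one that SAP 6.8 already permits.

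**What to change.** Keep the by-visit table and add the following to SAP 7.3.4.

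- **A worst post-baseline summary.** For each subject, take the maximum QTcF and the maximum change from baseline over all scheduled and unscheduled ECGs from first dose to 30 days after last dose, including extra ECGs at scheduled visits. Use the mean of the available replicates at each timepoint. Report the number and percentage of subjects in the existing bands. This also settles the Day 15 count, because a subject is counted once, at the highest of the three readings or of any later one.
- **An ECG listing** showing scheduled and unscheduled readings.
- **A footnote** stating that ECGs after Cycle 1 Day 15 are for-cause, so the summary gives observed outliers and not systematic coverage of later treatment.

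The cost is one extra table and one listing from data already held. No new ECGs and no change to clinical management are needed. The downside is that the outputs mix systematic Day 15 readings with for-cause ones, so the percentages must not be read as incidence over the whole treatment period. The footnote and the retained by-visit table limit that risk.
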